### 4.2 Visit procedures

The study will involve three clinic visits (with the option for a separate screening visit before visit 1) and four follow up telephone calls. Visits and blood draws will be coordinated with regular follow up visits in the oncology clinic wherever possible. Procedures are summarized in Table 3.

**Table 3. Schedule of Study Activities**

Procedures for patients	Visit 1	Follow up Phone call 8-10 days post V1	Follow up Phone call 30-33 days post	Visit 2 2 months Post V1†	Follow up Phone call 8-10 days post V2	Follow up Phone call 30-33 days post V2	Visit 3 12-15 months post V1
-------------------------	---------	--	--------------------------------------	---------------------------	--	---	------------------------------

			V1				
Informed Consent	X*						
Past Medical History	X*						
Current Health Status	X*						
Medications	X*						
Review of Immunization Records	X*						
Vital signs	X						
Immune Markers (CBC, qIgs, T and B subsets)	X						
Vaccine serologies	X			X			X
PCV13 and DTaP Immunization	X						
PPV23 immunization				X			
Phone Call (adverse events)		X	X		X	X	

qIgs: quantitative immunoglobulins; \*Maybe be conducted as part of a screening visit at 3-5 months post-treatment. †Visit can occur up to 3 months post-immunization.

#### Visit 1 (Baseline assessment):

After providing informed consent, participants with ALL will undergo a standardized health evaluation, including review of past medical history, current health status, and medications, and vital signs as part of routine clinical care. Immunization records will be obtained from the participant's vaccination card, medical chart, family physician or public health. Varicella serology results at time of ALL diagnosis (measured as part of routine care) will be obtained from the medical record. The above activities can be completed as part of a separate screening visit at 3-5 months post-treatment, with visit 1 then scheduled at 6 months post-treatment to collect bloodwork and administer immunizations.

Baseline laboratory evaluation will include complete blood count, quantitative serum immunoglobulins (IgA, IgG, IgM), peripheral blood T and B cell subsets and antibody titres to the following vaccine antigens: tetanus toxoid, pertussis toxin (PT), varicella, and pneumococcal serotype-specific IgG. If serum immunoglobulins, T and B cell subsets or antibody titres were measured within one month prior to enrollment, those results can be obtained as baseline results, in lieu of repeating the testing.

Participants will be immunized with PCV13, DTaP-IPV-Hib (If DTaP-IPV-Hib is not available, DTaP-IPV and Hib may be administered separately) in addition to the "catch-up" vaccines

required according to the schedule currently followed at their centre. Vaccines will be administered in the SIC or oncology clinic, where possible, but may be administered by the primary care physician or public health. Vaccines must be administered within two months of the baseline assessment and within 12 months of completing chemotherapy. The SIC nurse will obtain vaccination details from the vaccine provider within 7 days of the vaccination visit.

Telephone follow-up for AEFI:

A study nurse will contact caregivers (or participants where appropriate) by telephone on days 8-10 and 30-33 after each immunization to elicit local and systemic symptoms and their severity using a standard questionnaire.

Visit 2 (2 months post-immunization)

Serologic responses will be measured to tetanus, PT and pneumococcus. PPV23 will be administered. If necessary, this visit can be delayed to 3 months post-immunization.

Visit 3 (12-15 months after visit 1):

Serologic responses will be measured to tetanus, PT and pneumococcus.

Blood sampling will be coordinated with routine blood draws, which are conducted at most follow up visits.

Controls:

Past medical history will be reviewed for any excluding conditions and once informed consent has been obtained, immunization records will be obtained as described above. Serum will be collected to measure “baseline” antibody titres to tetanus, PT, varicella, and pneumococcal serotypes, based on the vaccinations received. There will be no further follow-up of controls.

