There is increasing evidence that antibody titres to vaccine antigens decrease over time in children who were fully vaccinated prior to chemotherapy.[23-26] A systematic review found that 25-35% of patients who had completed chemotherapy had antibody levels to tetanus and diphtheria that were below protective levels and 70% were susceptible to pertussis.[26] Among 80 children with ALL treated between 2001 and 2010, approximately 30% of those who were seropositive to measles and 17% who were seropositive for varicella at diagnosis subsequently lost immunity to those antigens.[25] In another study of 100 ALL patients who were a mean of 2 years post-chemotherapy, only 42-86% had protective titres to routine childhood vaccines including Hib, hepatitis B, diphtheria and rubella, compared to 96-100% of healthy controls.[23] Seventy-three percent of subjects had non-protective titres to  $\geq 2$  antigens. Studies conducted prior to the introduction of universal infant pneumococcal conjugate vaccination (PCV) reported that pneumococcal antibody concentrations were significantly lower in children with ALL who were 3-6 months post-chemotherapy compared to age-matched healthy controls.[27, 28] No published studies have evaluated the impact of infant PCV immunization on pneumococcal titres post-chemotherapy.

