#### *Exclusion criteria*

- Infantile ALL
- Evidence of disease relapse or secondary malignancy
- History of underlying primary immunodeficiency
- Transplant recipient
- Received intravenous immunoglobulin (IVIG) within past 9 months or other blood products within the prior 3 months.
- Children who received PPV23 within 12 months of enrollment will not be eligible to receive PCV13 or PPV23. These children can still participate in the baseline evaluation, receive DTaP-Hib-IPV vaccine, and have tetanus and pertussis serology measured at 2 and 12-15 months post-immunization.

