#### 4.3.2 Serologic testing

Up to 5 mL of whole blood will be collected in a serum separator tube by venipuncture. After collection, blood will be kept at room temperature for 30 minutes to clot. Blood will then be centrifuged for 10 minutes at approximately 2500 RPM. Serum will be separated, aliquoted and frozen at -20°C in the local clinical or research laboratory.

Samples will be batch shipped on dry ice to the Canadian Center for Vaccinology's research laboratory at the IWK Health Centre in Halifax, NS approximately every 3-6 months where they will be stored at -80°C until they are processed locally and/or shipped to other laboratories as below.

Tetanus, pertussis toxoid and varicella IgG measurement will be conducted at the Canadian Center for Vaccinology laboratory using validated enzyme immunoassays.

Pneumococcal serotype-specific IgG levels to vaccine serotypes will be measured at McGill University Health Centre.

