### **6.2 Sample size and Power**

Approximately 278 new cases of ALL are diagnosed annually in Canadian children <15 years of age.[1] We estimate that approximately 50-60% of children diagnosed with ALL will complete chemotherapy, and consent to participate in the study. We expect to recruit 75–80 children over the enrollment period. To ensure adequate power (>75%) to assess differences in vaccine responses according to treatment protocol, at least 30 subjects will be recruited from centres using DCFI protocols, with the remainder recruited from COG centres. Seventy-five age-matched control subjects will be recruited. If at least 60% of controls have protective antibody titres, a sample of at least 75 cases will give 77% power to detect a  $\geq 20\%$  absolute difference in the proportion of cases achieving seroprotection. This sample size will also give 90% power to detect a standardized difference in mean log titre of  $\geq 0.53$  between cases and controls.

*Safety assessment:* With a total sample size of 75 vaccinees, the probability of detecting at least one occurrence of an AEFI that occurs at a frequency of  $\geq 2\%$  in the population is 0.78 and the probability of detecting an AEFI that occurs at a frequency of  $\geq 1\%$  in the population is 0.53.

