### **6.3.2 Independent variables**

**Demographics:** Patient's month/year of birth, sex, province of residence

**Medical history:** Age at diagnosis of ALL, disease risk category (standard risk, high risk or very high risk), treatment protocol used, time to disease remission, total length of treatment, current disease status, vaccine-preventable infections (before and after re-immunization).

**Immunization history:** number of doses of each vaccine received prior to ALL diagnosis and while receiving chemotherapy, vaccine products received, age at immunization, type of vaccine provider, interval from last chemotherapy to immunization, and varicella serology results at ALL diagnosis.

**Immunologic status:** absolute lymphocyte count, total IgG level; total T cells, CD4+ T cells, CD8+ T cells, CD4/CD8 T cell ratio, memory and naïve T cells; total, memory and naïve B cells, NK cell counts.

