## **6.4 Statistical Methods**

**Immune responses:** Immune markers (see 5.2) will be compared to age-specific reference values. Baseline GMTs with 95% confidence intervals and proportion with protective titres at baseline will be reported for cases and controls, stratified by interval since last vaccination. Varicella titers will be compared pre-chemotherapy (i.e., at diagnosis) and post-chemotherapy and the proportion with loss of immunity will be reported. The proportion of subjects with GMT ratios  $\geq 4$  or protective titres at 2 and 12-15 months post-vaccination will be reported for pneumococcal vaccines (PCV13+PPV23) and DTaP-IPV-Hib, stratified by age, ALL treatment protocol (COG versus DFCI), interval from last chemotherapy to immunization, and ALL risk category. Vaccine responses will be compared to the expected responses in healthy children based on published clinical trials. Differences among categorical variables will be assessed by Pearson's  $\chi^2$  test or with Fisher exact test when expected cell sizes are  $< 5$ . Independent predictors of low baseline GMTs to tetanus toxoid and pneumococcal serotypes and of an adequate immune response to PCV13+PPV23 vaccination and DTaP-IPV-Hib booster will be assessed using multivariable regression models.

**Safety assessment:** The frequency of low impact, moderate impact and high impact or serious AEFI will be reported by vaccine type, age and ALL risk category, and compared to the published frequencies in healthy children. The frequency of events deemed to be related to vaccination based on the causality algorithm will also be reported.

All statistical analyses will be conducted using SAS® version 9.4 (Cary, NC).

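### The varicella result at diagnosis carries no blood-product condition, although the study sample paired with it does, so the reported loss of immunity can be biased upward by an unknown amount

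*Combined protocol and SAP*

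**What the plan says.** Section 4.2, Visit 1, sets the source of the earlier measurement: "Varicella serology results at time of ALL diagnosis (measured as part of routine care) will be obtained from the medical record". No condition is placed on what the child had received before that sample. Section 6.3.2 lists "varicella serology results at ALL diagnosis" under immunization history. It does not list the sample date or any IVIG or transfusion history.

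Section 6.4 states the use: "Varicella titers will be compared pre-chemotherapy (i.e., at diagnosis) and post-chemotherapy and the proportion with loss of immunity will be reported". No exclusion, flag or sensitivity analysis goes with it.

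The later measurement is treated differently. Section 3.2.1 excludes a case who "Received intravenous immunoglobulin (IVIG) within past 9 months or other blood products within the prior 3 months", and 3.2.2 applies the same rule to controls. The later assay is specified in 4.3.2: "Tetanus, pertussis toxoid and varicella IgG measurement will be conducted at the Canadian Center for Vaccinology laboratory using validated enzyme immunoassays". The assay behind the diagnosis result is not stated.

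**The concern.** Loss of immunity is read from a before-and-after pair: positive at diagnosis, negative after chemotherapy. The protocol does not explain its IVIG and blood-product exclusions, but in a serology study their natural purpose is to keep donor antibody out of the measured titres. That safeguard covers only the second half of the pair.

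A child with no varicella immunity whose diagnosis sample was drawn after a blood product could test positive on donor antibody. Years later the same child tests negative and enters the numerator, although no immunity was lost. Identical assays at both times would not prevent this. Since neither the sample date nor earlier products are listed variables, the analyst could not tell from the listed data whether it had happened. At stake is how far the reported loss proportion can be trusted.

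**Working it through.** The plan gives no figure for varicella loss, so there is none to reproduce. The power figures in 6.2 concern cases versus controls and do not bear on this point.

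**1. Can the exclusion windows reach the diagnosis sample?** Section 1.1.1 puts treatment at about 2 years for girls and 3 years for boys. Section 3.2.1 enrolls cases 3 to 12 months after chemotherapy. Diagnosis therefore lies about 24 + 3 = 27 to 36 + 12 = 48 months before enrollment. The longer window is 9 months, so it cannot.

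**2. Inputs.**
- N = 80, the upper end of 6.2: "We expect to recruit 75–80 children over the enrollment period".
- L = 17%, the true loss rate. This is illustrative, from 1.2: "approximately 30% of those who were seropositive to measles and 17% who were seropositive for varicella at diagnosis subsequently lost immunity".
- s, the share truly seropositive at diagnosis. Assumed: 0.90 or 0.625 (50 of 80).
- f, the share of true seronegatives who read positive at diagnosis from passive antibody and negative later. Assumed: 20 to 50% had a product before the draw and half of those read positive, so f = 0.20 × 0.5 = 0.10 to 0.50 × 0.5 = 0.25.

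**3. Formula.** Reported loss = [sL + (1 − s)f] / [s + (1 − s)f]. The excess over L is (1 − s)f(1 − L) / [s + (1 − s)f], which is positive whenever f > 0, s < 1 and L < 1.

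**4. Results for 80 cases.**

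| Truly positive / negative | True losses | f | False losses | Reported loss |
|---|---|---|---|---|
| any | 17% of positives | 0 | 0 | 17.0% |
| 72 / 8 | 12.24 | 0.10 | 0.8 | 13.04/72.8 = 17.9% |
| 72 / 8 | 12.24 | 0.25 | 2.0 | 14.24/74 = 19.2% |
| 50 / 30 | 8.5 | 0.10 | 3.0 | 11.5/53 = 21.7% |
| 50 / 30 | 8.5 | 0.25 | 7.5 | 16/57.5 = 27.8% |

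A much harsher pair of assumptions, s = 0.5 and f = 0.50, gives (6.8 + 20)/(40 + 20) = 44.7%. Nothing in the documents supports that setting. It shows only that the result is governed by two quantities the plan does not supply.

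**5. Seroconversion before the study sample.** If a fraction g of the false positives become truly positive through infection or vaccination, they enter the denominator but not the numerator. With h the share of true seronegatives who read positive at diagnosis, the excess becomes (1 − s)h(1 − g − L) / [s + (1 − s)h]. At L = 17% this stays upward unless g exceeds 83%.

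**The case against.** The strongest reply is that the premise is not in the documents. They do not say that any child receives a blood product before the diagnosis serology, or how often. Section 6.4 places the sample before chemotherapy, and its order relative to any transfusion is unknown. A reader might infer that antibody from transfusions will in fact be reported as immunity destroyed by chemotherapy. The text does not support that: the mechanism is possible, its occurrence is not shown, and 6.4 speaks of loss without naming a cause. This part of the objection stands.

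A reader might also infer that age at diagnosis would falsely appear as a risk factor for loss. The plan has no such analysis. The models in 6.4 cover low baseline titres to tetanus and pneumococcal serotypes, and responses to the study vaccines. The first objective does name varicella, but its outcome is the post-chemotherapy titre, which the exclusions protect. Section 6.3.1 does not list loss of varicella immunity as an outcome.

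Three further points have weight:
- The illustration depends on s, and with 90% truly seropositive the shift is one or two percentage points. Against that, 1.2 says most children diagnosed under age 5 have not completed preschool immunization, and 3.2.1 does not require varicella vaccination, so some true seronegatives are to be expected.
- The cited 17% is defined in the same way, so it may already contain the same artefact.
- The Wilson 95% interval for 8.5 of 50 is about 9 to 30%, so the illustrated shifts lie within sampling error. That limits their practical weight, but an interval does not correct a bias.

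Finally, 6.3.2 is a list of independent variables and not the case report form, and past medical history is collected at Visit 1. Transfusion history around diagnosis is therefore unspecified, not shown to be uncollected. Even so, 6.4 makes no use of it.

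**Conclusion.** The point holds as a design asymmetry with a probable direction and an unknown size. The protocol's own safeguard applies to one half of the pair, and no listed variable or planned analysis covers the other half. If passive positives occurred at diagnosis, the reported proportion would be too high, unless more than 83% of those children seroconverted before the study sample.

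The bias is zero if the samples precede any product. From an assumed true 17%, reported loss is about 18 to 19% with 90% truly seropositive and about 22 to 28% with 62.5%, at f = 0.10 to 0.25. Both s and f are assumptions. The effect is confined to one descriptive proportion. The primary outcomes, the case-control varicella comparison and the planned models are untouched. It is a cheap improvement worth making, not a threat to the trial's conclusions.

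**What to change.** When the diagnosis serology is abstracted, also record the date of that sample and the dates of any IVIG or other blood product given before it. In 6.4, report the proportion with loss of varicella immunity twice: for all pairs, and for pairs whose diagnosis sample was free of IVIG in the previous 9 months and of other blood products in the previous 3 months, which are the protocol's own windows. State in advance that any conclusion about loss will rest on the restricted figure if the two differ materially.

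The cost is two extra fields from a chart already being read and a sentence or two in 6.4, with no added blood draw. The restricted figure loses precision. If 20 to 50% of 50 seropositive pairs dropped out, 40 to 25 would remain, and the half-width 1.96 × √(0.17 × 0.83/n) would grow from 10.4 points to between 11.6 and 14.7. Restriction also discards truly immune children who had received a product and may select a different kind of patient, which is why both figures should be shown. It does not address a change of assay between the two samples, which is a separate gap.

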#### 4.3.1 Immunologic assessment

##### *Quantitative immunoglobulins*

Up to 5 ml of whole blood will be collected for baseline quantitative measurement of total IgA, IgG and IgM levels. Samples will be processed at the local clinical laboratory according to standard procedures and denominated results will be transferred to the coordinating centre. At some centres this testing is conducted as part of routine clinical care.

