##### *Lymphocyte subsets*

Up to 5 ml of whole blood will be collected for baseline quantitative measurement of T, B and NK lymphocyte subsets. Samples will be processed for flow cytometry at the local laboratory according to standard procedures and denominated results will be transferred to the coordinating centre.

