invasive pneumococcal disease, tetanus, diphtheria and pertussis. Their immunological and serological test results will be shared with site investigators who will discuss them with the primary oncologist, participant and family, as appropriate for clinical care. However, due to the need batch samples and to test pre and post-vaccination samples concurrently for some assays, results may not be available in a timely manner. The information learned from this study will support the development of immunization guidelines for patients with ALL that will lead to improvements in care. In this study, the benefits outweigh the potential harms.

For control participants, participation in this study involves minimal to low risk. Participants who already require venipuncture for another indication will only be asked to agree to have a small additional sample (3-10 ml) drawn for study purposes. The only risk is related to a breach of their confidential information which will be minimized by the measures outlined below. For participants undergoing venipuncture only for the purposes of this study, the potential harms include pain, bleeding, or bruising, fainting, and very rarely, infection. These discomforts are brief and transient. There will be no direct benefits to controls.

Individual results will not be routinely available to healthcare providers of controls as the clinical relevance of such results in immunocompetent children following the routine immunization schedule is uncertain. However, if the principal and/or site investigator determines that antibody titers are sufficiently low to raise concerns regarding an unidentified health problem in a participant, the results will be sent to the primary care provider with recommendation for follow up and/or referral for further evaluation.

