## **7.3 Informed Consent Process**

The consent form will be reviewed with caregivers by the SIC nurse, research coordinator, the oncologist or oncology clinic nurse. All participants/controls or their primary caregiver will be asked to consent to the following: permit study staff to access the patient's chart and contact other healthcare providers as necessary to retrieve immunization records and other clinical information, collection of additional blood for serology, transfer specimens and clinical data to the coordinating centre in Halifax (CCfV) and to send serum specimens to McGill University for pneumococcal serotype-specific IgG testing (if necessary). Some participants (ALL and controls) will also be asked to consent to venipuncture for study bloodwork, if venipuncture is not required for routine blood work. Consent will also be sought to allow future contact for participation in other studies.

In addition to the above, participants with ALL or their caregivers will be asked to consent to: administration of PCV13, PPV23 and DTaP-IPV-Hib vaccines, and telephone and/or email contact from study team to collect information on AEFI. Those who have contraindications to or refuse one or two specific vaccines may still be included in the study. Participants and caregivers' questions will be answered and written informed consent will be obtained.

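### Section 4.2 lets an earlier antibody titre stand as a case's baseline without requiring that it come from the study assay

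*Combined protocol and SAP*

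**What the plan says.** Section 4.2, Visit 1, lists the baseline tests for children with ALL, including titres to tetanus, pertussis toxin, varicella and the pneumococcal serotypes. It then covers three kinds of test in one sentence. Alongside immunoglobulins and lymphocyte subsets, that sentence provides for the case where "antibody titres were measured within one month prior to enrollment, those results can be obtained as baseline results, in lieu of repeating the testing". It sets no condition on laboratory, assay, units or retained serum.

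The three kinds of test are handled differently elsewhere:

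- Immunoglobulins (4.3.1): "Samples will be processed at the local clinical laboratory according to standard procedures".
- Lymphocyte subsets (4.3.1): "Samples will be processed for flow cytometry at the local laboratory according to standard procedures".
- Vaccine titres (4.3.2): "Tetanus, pertussis toxoid and varicella IgG measurement will be conducted at the Canadian Center for Vaccinology laboratory using validated enzyme immunoassays", and "Pneumococcal serotype-specific IgG levels to vaccine serotypes will be measured at McGill University Health Centre".

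Table 3 marks "Vaccine serologies" at Visits 1, 2 and 3. Section 7.1 explains that results may be delayed partly because of the need to "test pre and post-vaccination samples concurrently for some assays". Controls have serum collected and measured (4.2, Controls), and no substitution rule is given for them.

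**The concern.** For the two locally run tests, accepting a recent local result fits the design. For vaccine titres it does not, because the study measures them in designated laboratories. A result that exists before enrolment would ordinarily come from clinical care, so it could come from a different assay or run than the same child's Visit 2 and Visit 3 titres and the controls' titres.

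Two uses of the baseline are exposed. In the post/pre ratio, an assay difference in the denominator looks like a larger or smaller vaccine response. In the comparison with controls, the difference can arise on the case side only, so it would not cancel between groups. A site doing this would be following the protocol, so it would not be a deviation.

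**Working it through.** No stated figure is in dispute. The check is whether any text limits the permission, and then which analyses use the value.

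**Step 1. Does anything limit the permission?**

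| Place | What it establishes | Limits the permission? |
|---|---|---|
| 4.2, Visit 1 | Earlier titres may replace testing, within one month before enrolment | Time window only |
| Table 3 | Serology is scheduled at Visit 1 | No |
| 4.3.2 | Named laboratories; validated enzyme immunoassays for tetanus, pertussis and varicella | No; the exception is not mentioned |
| 7.1 | Paired pre/post testing for some assays, not named | No |
| 7.3 | Consent to send serum for pneumococcal IgG, only where needed | No |
| 6.4 | Statistical methods | No rule to flag or exclude such a value |

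**Step 2. Which analyses use the baseline titre?**

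| Analysis | Uses baseline? |
|---|---|
| Primary: proportion at or above 0.35 µg/ml at 2 and 12-15 months (6.3.1) | No |
| Primary: same proportion at baseline, cases versus controls (6.3.1) | Yes, case side only |
| Secondary: baseline varicella, pertussis toxin and tetanus versus controls (6.3.1) | Yes, case side only |
| Secondary: ratio of at least 4 for DTaP (5.2, 6.3.1); also reported for pneumococcal vaccines (6.4) | Yes, as denominator |
| Models for low baseline tetanus and pneumococcal titres (6.4) | Yes, as outcome |

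Varicella is not measured at Visits 2 and 3, so it has no fold-rise.

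**Step 3. Effect on one child.** Let f be the factor by which the outside assay reads relative to the study assay. Then

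observed ratio = post / (f × true baseline) = true ratio / f,

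so the child counts as a responder only if the true ratio is at least 4f. The documents give no value for f. As assumed values:

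- f = 2: true ratio needed 4 × 2 = 8; a true 4-fold rise reads as 4/2 = 2, a non-responder.
- f = 1.5: true ratio needed 4 × 1.5 = 6.
- f = 1: no change.
- f = 0.5: true ratio needed 4 × 0.5 = 2; a true 2-fold rise reads as 4, a responder.

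**Step 4. Bound for the group.** A substituted value can change at most that child's own classification. With 75 cases (6.2), one child moves a proportion by at most 1/75 = 1.3 percentage points, and k children by at most k/75, which is the share of cases substituted. With no substitution the effect is zero. Assays that err in opposite directions would partly cancel. The documents supply neither k nor f, so no narrower figure can be justified.

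**The case against.** The strongest reply is that the rest of the plan points to central testing: scheduled Visit 1 serology, named laboratories, and paired testing for some assays. The permission is optional and limited to one month. The only sign that outside titres exist is the survey in 1.3.1, where one of ten responding centres measures titres routinely after chemotherapy and a respondent at another does so as personal practice. The survey does not say which antigens are tested, or whether either centre is a study site. The exception also serves a real aim: 7.1 commits to the least additional blood and notes the discomfort of venipuncture for children who would otherwise need only a fingerstick.

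Much of this stands. It shows that exposure is undemonstrated and probably limited. It does not close the gap, because the sentence is an express exception to repeat testing and names antibody titres.

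Three stronger readings should be resisted:

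- A reader might infer that the primary outcome is biased. Two of its three time points do not use the baseline, and nothing shows that pneumococcal IgG would be substituted at all.
- A reader might infer that a substitution could never be traced. Section 6.4 is silent, but the case report forms are not among the documents and may record laboratory and sample date.
- A reader might infer that earlier local immunoglobulin and subset results are interchangeable with Visit 1 results. They come from the kind of laboratory the plan intends, but the window runs from enrolment. If enrolment were dated from consent at a 3-month screening visit, with Visit 1 at 6 months, a result could be about 3 + 1 = 4 months old.

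**Conclusion.** The point holds as a gap in the wording: a site following section 4.2 as written may use a non-study titre as a case's baseline, and no other section prevents it. The exposed analyses are the fold-rise of at least 4, the case side of the baseline comparison with controls, and the models for low baseline titres. The primary proportions at 2 and 12-15 months are not affected.

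The frequency of substitution and the size and direction of any effect are unknown, and the effect may be small or zero. The documents do not support a claim of actual bias or any estimate of it beyond the bound of one child in 75 per substitution. That bound assumes 75 analysed cases and would be larger per child with fewer. This is a minor priority, worth correcting because the change is simple and costs little.

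**What to change.** In section 4.2, delete antibody titres from the substitution sentence so that it covers only immunoglobulins and T and B cell subsets. Then add:

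> Baseline vaccine titres are measured with the study assays (4.3.2) on pre-vaccination serum: either Visit 1 serum or stored serum from an earlier draw within the permitted window that has actually been tested with the study assay. A titre from any other assay is not used as the baseline value in the fold-rise or case-control analyses.

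A routine post-chemotherapy varicella result may be kept in addition, for the comparison in 6.4 with the result at diagnosis, which itself comes from routine care.

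**Cost.** One deletion and two added sentences. Visit 1 serology is already in Table 3, takes up to 5 mL of the 15 mL ceiling for that visit (4.3, 4.3.2), and is among the laboratory costs (8.1.2). Sample size, power, vaccines and visit timing do not change. The blood count is not on the substitution list, so some blood is taken at Visit 1 anyway, although 7.1 notes that a fingerstick can suffice for it. The real downside is a serology tube of up to 5 mL in a few children who would otherwise have used an earlier result, to be weighed against the minimum-volume commitment in 7.1. The stored-serum option reduces that burden.
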